3.6 Discontinuation of investigational product

Subjects may be discontinued from investigational product (IP) in the following situations:

- Subject decision. The subject is at any time free to discontinue treatment, without prejudice to further treatment
- Adverse Event (eg, Risk to patients as judged by the investigator and /or AstraZeneca)
- Pregnancy
- Severe non-compliance with the study protocol as judged by the investigator and/or AstraZeneca

- Patient incorrectly initiated on investigational product
- Objective disease progression or subject is no longer receiving clinical benefit
- Subject loss to follow-up

3.6.1 Procedures for discontinuation of a subject from investigational product

At any time, subjects are free to discontinue investigational product or withdraw from the study (ie, investigational product and assessments – see Section 3.7), without prejudice to further treatment. A subject that decides to discontinue investigational product will always be asked about the reason(s) and the presence of any adverse events. If possible, they will be seen and assessed by an Investigator(s). Adverse events will be followed up (See Section 6); and all study drugs should be returned by the subject.

Any subject who discontinues study treatment for reasons other than objective disease progression should have tumour assessments performed as scheduled in the protocol (See Table 1 and Table 2) until objective disease progression is documented or death occurs, unless consent is withdrawn. Study procedures related to PROs, SAEs and anti-cancer treatment must be captured until the subject no longer has RECIST 1.1 assessments (disease progression or permanent withdrawal from the study).

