^d Taken following progression on the latest line of therapy. The collection of this tumour tissue sample for central mutation analysis is not included in the 28-day screening period.

^e The optional second tumour tissue sample can be taken as part of the same procedure as the mandatory screening biopsy for mutation analysis.

^f Archival tumour sample only to be submitted after T790M positive status confirmed by central testing. Not required for T790M negative patients.

^g To be completed pre-dose.

^h If screening assessments are not done at Visit 2, but have been done at Visit 1 and have been performed within 14 days window prior to starting study treatment, with no change in condition and no clinical indication to do so, they do not have to be repeated on Visit 2 if subject's condition has not changed. (except for fasting glucose).

ⁱ To be taken at the same time as the screening biopsy is taken or prior to mutation screening. All plasma samples are required by AstraZeneca, regardless of the outcome of the mutation screening.

^j Collect every 6 weeks up to and including progression (corresponding with the RECIST assessments – and continuing after treatment discontinuation in absence of disease progression).

^k If for any reason the sample is not drawn prior to first dose it may be taken at any visit until the last study visit.

^l To be obtained at one time point at any time from Cycle 2 Day 1 onwards

^m If only one measurable lesion exists, it is acceptable to be used as long as it has not been previously irradiated, and baseline tumour assessment scans are done at least 14 days after the screening biopsy is performed.

ⁿ Assess every 6 weeks relative to first dose until end of study (including survival follow-up period) and at the time of progression.

^o Assess every 3 weeks relative to first dose until end of study (including survival follow-up period) and at the time of progression.

^p PRO-CTCAE will only be administered in those countries where a linguistically validated version exists.

^q Assessed at Cycle 7 Day 1 then every 3 weeks relative to first dose thereafter until end of study (including survival follow-up period) and at the time of progression.

^r Following AZD9291 discontinuation, SAEs considered related to study procedures should continue as outlined in Table 6.

^s Survival status including anti-cancer treatment to be performed every 6 weeks (relative to first dose) following disease progression or withdrawal from treatment.

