EORTC QLQ-C30 and EQ-5D-5L (by electronic device)	← X (every 6 weeks until end of study and at the time of progression) relative to first dose →					5.3.2.1 & 5.3.2.2
EORTC QLQ LC13 (by electronic device)	← X (every 3 weeks until end of study and at the time of progression) relative to first dose →					5.3.2.1
PRO-CTCAE (by electronic device)	← X (every 3 weeks until end of study and at the time of progression) relative to first dose →					5.3.2.3
Healthcare Resource Use	← →					5.3.2.5
Dispense study medication	X					3.3 & 7.2
Dose with AZD9291	Daily dosing					7.2
Concomitant medication & procedures	← →					7.7

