4.3.4 Survival follow-up

- Assessments for survival should be made every 6 weeks (relative to first dose) following objective disease progression or withdrawal from treatment. Survival information may be obtained via telephone contact with the patient, patient's family or by contact with the patient's current physician. In addition to the survival status, the following assessments are also required post progression as detailed in the study plan (see [Table 1](#) and [Table 2](#)):
- EORTC QLQ-C30 and EQ-5D-5L every 6 weeks.
- EORTC QLQ LC13 and PRO-CTCAE every 3 weeks.
- Anti-cancer therapy collected every 6 weeks.
- Subsequent response/progression data every 6 weeks until the first confirmed disease progression on a subsequent treatment.

Survival data will be collected up to the time of the final OS analysis. Patients should be contacted in the 2 weeks following the data cut-off for the final survival analyses to provide complete survival data.

The status of ongoing, withdrawn (from the study) and "lost to follow-up" patients at the time of an overall survival analysis should be obtained by the site personnel by checking the patients notes, hospital records, contacting the patients general practitioner and checking publicly available death registries. In the event that the patient has actively withdrawn consent to the processing of their personal data, the vital status of the patient can be obtained by site personnel from publicly available resources where it is possible to do so under applicable local laws.

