For each of the symptoms scales/items in QLQ LC13, time to symptom deterioration will be defined as the time from enrolment until the date of first clinically meaningful symptom deterioration (an increase in the score from baseline of ≥ 5) or death (by any cause) in the absence of a clinically meaningful symptom deterioration, regardless of whether the patient withdraws from study therapy or receives another anticancer therapy prior to symptom deterioration. Death will be included as an event only if the death occurs within two visits of the last PRO assessment where the symptom change could be evaluated.

Patients whose symptoms (as measured by QLQ LC13) have not shown a clinically meaningful deterioration and who are alive at the time of the analysis will be censored at the time of their last PRO assessment where the symptom could be evaluated. Also, if symptoms progress after two or more missed PRO assessments or the patient dies after two or more missed PRO assessments, the patient will be censored at the time of the last PRO assessment where the symptom could be evaluated. If a patient has no evaluable assessments or does not have baseline data they will be censored at day 1. The population for analysis of time to symptom deterioration will include a subset of the FAS population who have baseline scores ≤ 95 .

Symptom Improvement Rate

The symptom improvement rate will be defined as the number (%) of patients with two assessments at least 18 days apart (ie, 21 days allowing a visit window of 3 days) which showed a clinically meaningful improvement (a decrease from baseline score > 5 for LC13 scales/items or > 10 for C30 scales/items) in that symptom from baseline. The denominator

will consist of a subset of the FAS population who have a baseline symptom score ≥ 5 (LC13 scales/items) or ≥ 10 (C30 scales/items).

Time from enrolment to second progression (PFS2) (exploratory)

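### Section 3.6.1 ends PRO, SAE and anti-cancer-treatment capture at progression for patients who stop AZD9291 early, against Tables 1, 2 and 6 and Section 4.3.4; where sites follow it, time to symptom deterioration could be modestly biased

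*Protocol*

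**What the plan says.** Section 3.6.1 sets a rule for one group: "Any subject who discontinues study treatment for reasons other than objective disease progression should have tumour assessments performed as scheduled in the protocol". Its last sentence then fixes how long other data are collected: "Study procedures related to PROs, SAEs and anti-cancer treatment must be captured until the subject no longer has RECIST 1.1 assessments (disease progression". The parenthesis goes on to name permanent withdrawal from the study as the alternative end.

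Other current parts of the protocol go further:

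- Table 1, footnote n (QLQ-C30, EQ-5D-5L): "Assess every 6 weeks relative to first dose until end of study (including survival follow-up period) and at the time of progression".
- Table 1, footnote o (QLQ LC13, and PRO-CTCAE in follow-up): "Assess every 3 weeks relative to first dose until end of study (including survival follow-up period) and at the time of progression". Footnote q sets the same end for PRO-CTCAE.
- Table 1, footnote s: "Survival status including anti-cancer treatment to be performed every 6 weeks (relative to first dose) following disease progression or withdrawal from treatment".
- Table 2, after 24 months post LSFD, for LC13: "X (every 3 weeks until end of study and at the time of progression) relative to first dose".
- Section 4.3.4, beyond survival status: "the following assessments are also required post progression as detailed in the study plan". It then lists the four questionnaires and, every 6 weeks, anti-cancer therapy.
- Table 6 keeps procedure-related SAEs in the survival follow-up period.

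None of these exempts patients who stopped AZD9291 early.

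Section 8.4 names the LC13 symptoms as the primary PRO outcome measures. It counts symptom deterioration "regardless of whether the patient withdraws from study therapy or receives another anticancer therapy prior to symptom deterioration", censors patients without deterioration at their last evaluable PRO, and counts a death only if it falls within two visits of that PRO.

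**The concern.** Section 3.6.1 is where a site looks when a patient stops the drug. It cites Tables 1 and 2 only for tumour assessments and does not point to Section 4.3.4. Read alone, it tells the site to stop the questionnaires at progression for a patient who stopped earlier because of, say, an adverse event. A patient who stopped at progression would go on completing them through survival follow-up. The protocol gives no reason for treating the two differently.

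Time to symptom deterioration is defined to run past treatment stop and past new therapy, so it needs post-progression questionnaires. If they end at progression, follow-up ends because of an event that may predict worsening. Questionnaires that were not completed cannot be recovered later, and no analysis rule repairs collection that differs between sites.

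**Working it through.** **The texts compared, for a patient who stopped AZD9291 before progression and has now progressed**

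| Data | Section 3.6.1 | Elsewhere |
|---|---|---|
| QLQ-C30, EQ-5D-5L | ends | every 6 weeks to end of study (Table 1 note n, Table 2, 4.3.4) |
| LC13, PRO-CTCAE | ends | every 3 weeks to end of study (Table 1 notes o and q, Table 2, 4.3.4) |
| Anti-cancer therapy | ends | every 6 weeks (Table 1 note s, 4.3.4) |
| Procedure-related SAEs | ends | continue (Table 6) |

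**What is lost if 3.6.1 is followed.** Section 4.3.3 and footnotes n, o and q require a PRO at progression, so worsening present then is kept. What is lost is deterioration that first appears later, and deaths more than two visits after the last PRO. Two visits are 2 × 3 = 6 weeks on the LC13 schedule, or 2 × 6 = 12 weeks if study visits after Cycle 7 Day 1 are meant. Patients who deteriorated before progression already have their event and add no bias.

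**Size.** The protocol states no figure to reproduce. It gives no early-stopping rate and no deterioration rate, so every input below is an assumption:

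- median PFS 9 months, so progression hazard μ = ln 2 / 9 = 0.0770 per month;
- median time to deterioration 12 months at the pre-progression hazard, so λ = ln 2 / 12 = 0.0578 per month;
- post-progression deterioration hazard kλ, with k = 1, 2 or 4;
- a fraction f stopping early, unrelated to prognosis, all of whose PROs end at progression;
- administrative censoring at 36 months.

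With full capture, for k ≠ 1 + μ/λ, the deterioration-free proportion is

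S(t) = exp[−(λ+μ)t] + μ exp(−kλt) × {1 − exp[−(μ+λ−kλ)t]} / (μ+λ−kλ).

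At t = 12:

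- k = 2: 0.198 + 0.206 = 0.405.
- k = 4: 0.198 + 0.109 = 0.307.

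Kaplan–Meier estimates at 12 months from 400,000 simulated patients per scenario, full capture versus capture stopped at progression in the early stoppers:

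| f | k = 2 | k = 4 |
|---|---|---|
| 5% | 40.4% vs 40.7% (+0.3) | 30.8% vs 31.3% (+0.5) |
| 10% | 40.5% vs 41.1% (+0.6) | 30.6% vs 31.7% (+1.1) |
| 20% | 40.5% vs 41.7% (+1.2) | 30.8% vs 33.2% (+2.4) |
| 30% | 40.6% vs 42.5% (+1.9) | 30.7% vs 34.4% (+3.7) |

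The simulated full-capture values agree with the formula. With k = 1 both estimates are 50.0% within simulation error, so there is no bias. The model does not treat deaths and the two-visit rule separately, and it does not use the discrete assessment grid.

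For scale, the 95% half-width for a proportion of 40% in 175 patients, before any loss to censoring, is 1.96 × √(0.4 × 0.6 / 175) = 0.073, or about 7 percentage points.

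**The case against.** The best defence is that 3.6.1 sets only a minimum for its own phase: data must be captured until RECIST assessments end, and Section 4.3.4 then takes over. The schedules and 4.3.4 all point the same way, so the intended design is not in doubt. That reading is possible. However, the sentence names progression as its end point and has no link to 4.3.4, so the text still needs reconciling.

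The objection does limit the consequence, and three stronger readings fail:

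- A reader might infer that time to symptom deterioration will be informatively censored. It would be only where a site follows 3.6.1 over the schedule, and only for patients not yet deteriorated at the progression PRO. Each LC13 single item has four levels, so it moves in steps of 100/3 = 33.3 points; dyspnoea, from three items, moves in steps of 100/9 = 11.1. Against a threshold of 5, one category of worsening is an event, and some patients will have had theirs before progression.
- A reader might infer that every patient who stops early is affected. Those who die or withdraw consent before progression are not, nor are those at sites that follow Table 1.
- A reader might infer that the subsequent-therapy endpoints lose their data. Footnote s and Section 4.3.4 require therapy data after progression. Section 5.8 separately requires second-progression status and time to subsequent treatment up to the RECIST modules freeze. These exploratory data are at risk only where 3.6.1 overrides all three.

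**Conclusion.** The contradiction is real and stands in current text. It is an inconsistency about data capture that should be corrected, not a flaw in the intended design. Its statistical effect is conditional: a modest bias in the favourable direction on a descriptive, single-arm secondary outcome, and only if sites follow 3.6.1 and worsening is more likely after progression. The range of about 0.3 to 3.7 percentage points at 12 months rests wholly on the assumed inputs, including that all early stoppers lose their post-progression questionnaires. The largest of these values is about half the sampling half-width of roughly 7 points. ORR does not depend on these data. The case for acting is that the lost questionnaires cannot be recovered and the correction is cheap.

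**What to change.** Replace the last sentence of 3.6.1 with a statement that, whatever the reason for stopping AZD9291 and unless consent is withdrawn:

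- PROs continue after progression as set out in Tables 1 and 2 and Section 4.3.4;
- subsequent anti-cancer therapy is captured as set out in Sections 4.3.4 and 5.8;
- SAEs are captured as set out in Table 6.

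Keep the RECIST modules freeze as the limit for the time-to-subsequent-treatment analysis, as Section 5.8, Table 9 and Section 8.7.6 require. Wording that ran this analysis to the final DCO would create a new conflict. Keep the consent-withdrawal limit explicit, since the sentence being replaced now carries it.

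The cost is one sentence in an amendment and a note to sites. The ePRO schedule and the survival contacts already exist, so no procedure is added beyond those the protocol already requires.

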3.7 Withdrawal from the study

The term withdrawal from the study refers to both discontinuation from study treatment and study assessments.

Patients may be withdrawn from the study for the following reasons:

- Screen failure
- Death
- Withdrawal of consent

If a patient wishes to withdraw their consent to both treatment and study assessments, they should be asked if they are willing to continue with survival follow-up (which can be conducted by telephone – see Section 4.3.4). If a patient wishes to withdraw their consent to further participation in the study entirely, including survival follow-up this should be clearly documented in the patient notes and in the clinical study database.

Withdrawn patients will not be replaced.

3.7.1 Screen failures

Screening failures are patients who do not fulfil the eligibility criteria for the study, and therefore must not receive AZD9291. These patients should have the reason for study withdrawal recorded as “Ineligible” (ie, patient does not meet the required inclusion/exclusion

criteria). This reason for study withdrawal is only valid for screen failures (not patients who have received AZD9291).

3.7.2 Withdrawal of the informed consent

Patients are free to withdraw from the study at any time (investigational product and assessments), without prejudice to further treatment.

Patients may withdraw from any aspects of the voluntary research (see Sections 3.7, 5.4 and 5.5) at any time, without prejudice to further treatment and independent of any decision concerning participation in other aspects of the main study

A patient who withdraws consent will always be asked about the reason(s) and the presence of any adverse events (AE). The Investigator will follow up AEs outside of the clinical study. The patient will return electronic PRO (ePRO) devices and unused study drug.

3.8 Termination of the study

The study may be stopped if, in the judgment of AstraZeneca study physician, trial subjects are placed at undue risk because of clinically significant findings that:

- meet individual stopping criteria or are otherwise considered significant
- are assessed as causally related to study drug,
- are not considered to be consistent with continuation of the study

Regardless of the reason for termination, all data available for the subject at the time of termination of follow-up must be recorded in the CRF. All reasons for discontinuation of treatment must be documented.

In terminating the study, the Sponsor will ensure that adequate consideration is given to the protection of the subjects' interests.

4. STUDY PLAN AND TIMING OF PROCEDURES

Table 1 Study Plan - Prior to 24 months post LSFD

Visit	Screening	Treatment Period (further treatment cycles as per Cycle 7)							Treatment Discontinuation	Follow-up Period			For details see Protocol Section
	1	2	3	4	5	6	7-9	10+		28-day follow-up	Progression follow-up	Survival follow-up	
Cycle ^a / Day		C1 D1	C1 D8	C1 D15	C2 D1	C3 D1	C4-6 D1	C7 ^b +D1	NA	NA	NA	NA	
Day	-28 to 1	1	8	15	22	43	64-106	127+	NA	NA	NA	NA	
Window (days) ^z	NA	0	±2	±2	±7	±7	±7	±7	0	±7	±7	±7	SECTION:
Informed consent ^c	X												3.3 & 4.1
Submit mandatory tumour tissue sample for mutation analysis ^d	X												4.1 & 5.6
Submit tumour tissue for diagnostic development (optional) ^e	X												4.1 & 5.6
Optional tumour biopsy for exploratory research									X ^u		X ^u		5.6
Archival tumour tissue ^f	X												5.6

Table 1 Study Plan - Prior to 24 months post LSFD

Visit	Screening	Treatment Period (further treatment cycles as per Cycle 7)							Treatment Discontinuation	Follow-up Period			For details see Protocol Section
	1	2	3	4	5	6	7-9	10+		28-day follow-up	Progression follow-up	Survival follow-up	
Cycle ^a / Day		C1 D1	C1 D8	C1 D15	C2 D1	C3 D1	C4-6 D1	C7 ^b +D1	NA	NA	NA	NA	
Day	-28 to 1	1	8	15	22	43	64-106	127+	NA	NA	NA	NA	
Window (days) ^z	NA	0	±2	±2	±7	±7	±7	±7	0	±7	±7	±7	SECTION:
Demography & baseline characteristics	X												4.1
Medical/surgical history	X												4.1
Inclusion/exclusion criteria ^x	X												3
Physical examination, including weight ^g	X	X ^g			X	X	X	X	X				5.2.3 & 5.2.6.2
Height	X												5.2.6.2
WHO Performance status ^g	X	X			X	X	X	X	X				4.1
Pregnancy test (pre-menopausal females only)	X												5.2.1

Table 1 Study Plan - Prior to 24 months post LSFD

Visit	Screening	Treatment Period (further treatment cycles as per Cycle 7)							Treatment Discontinuation	Follow-up Period			For details see Protocol Section
	1	2	3	4	5	6	7-9	10+		28-day follow-up	Progression follow-up	Survival follow-up	
Cycle ^a / Day		C1 D1	C1 D8	C1 D15	C2 D1	C3 D1	C4-6 D1	C7 ^b +D1	NA	NA	NA	NA	
Day	-28 to 1	1	8	15	22	43	64-106	127+	NA	NA	NA	NA	
Window (days) ^z	NA	0	±2	±2	±7	±7	±7	±7	0	±7	±7	±7	SECTION:
Ophthalmologic assessment	X	← as clinically indicated →											5.2.7.1
Vital signs [§]	X	X	X	X	X	X	X	X	X				5.2.6
Clinical chemistry ^y / Haematology/Urinalysis [§]	X	X ^h	X	X	X	X	X	X	X				5.2.1
Digital ECG	X	X			X	X	X	X	X				5.2.4
Echocardiogram/MUG A	X		← every 12 weeks(±1 week) relative to first dose →										5.2.5
Plasma sample for ctDNA ^g	X ⁱ	X	X	X	X	X	X		← every 6 weeks in line with RECIST assessments ^j →			4.3.3 & 5.6.2	
Optional genetic consent and sample	X ^k												5.5
Optional CSF sample					X (once only) ^l								5.4.1

Table 1 Study Plan - Prior to 24 months post LSFD

Visit	Screening	Treatment Period (further treatment cycles as per Cycle 7)							Treatment Discontinuation	Follow-up Period			For details see Protocol Section
	1	2	3	4	5	6	7-9	10+		28-day follow-up	Progression follow-up	Survival follow-up	
Cycle ^a / Day		C1 D1	C1 D8	C1 D15	C2 D1	C3 D1	C4-6 D1	C7 ^b +D1	NA	NA	NA	NA	
Day	-28 to 1	1	8	15	22	43	64-106	127+	NA	NA	NA	NA	
Window (days) ^z	NA	0	±2	±2	±7	±7	±7	±7	0	±7	±7	±7	SECTION:
Tumour assessments (RECIST v1.1) ^m	X ^v	every 6 weeks(±1 week) relative to first dose until disease progression 										4.2 & 5.1.1	
EORTC QLQ-C30 and EQ-5D-5L (by electronic device)		X ^g	every 6 weeks(±1 week) relative to first dose 					X		X ⁿ	X ⁿ	5.3.2.1 & 5.3.2.2	
EORTC QLQ LC13 (by electronic device)		X ^g	Weekly(±2days) relative to first dose 		every 3 weeks(±3 days) relative to first dose 			X		X ^o	X ^o	5.3.2.1	
PRO-CTCAE (by electronic device) ^p		X ^g	weekly(±2 days) for first 18 weeks of treatment 				X ^q	X		X ^o	X ^o	5.3.2.3	
Healthcare Resource Use												5.3.2.5	
Dispense study medication		X			X	X	X	X ^b					3.3 & 7.2

Table 1 Study Plan - Prior to 24 months post LSFD

Visit	Screening	Treatment Period (further treatment cycles as per Cycle 7)							Treatment Discontinuation	Follow-up Period			For details see Protocol Section
	1	2	3	4	5	6	7-9	10+		28-day follow-up	Progression follow-up	Survival follow-up	
Cycle ^a / Day		C1 D1	C1 D8	C1 D15	C2 D1	C3 D1	C4-6 D1	C7 ^b +D1	NA	NA	NA	NA	
Day	-28 to 1	1	8	15	22	43	64-106	127+	NA	NA	NA	NA	
Window (days) ^z	NA	0	±2	±2	±7	±7	±7	±7	0	±7	±7	±7	SECTION:
Dose with AZD9291		← Daily dosing →											7.2
Concomitant medication & procedures		← →											7.7
Adverse events ^w		← →									X ^t	X ^t	6.3 & 6.4
Survival Status												X ^s	4.3.4
Anti-cancer treatment	X										X	X ^s	4.3.3, 4.3.4
Subsequent response /progression data												X ^t	5.8

^a A cycle is defined as 21-day treatment period.

^b Visit schedule changes after Cycle 7 Day 1 from every 21 days (3 weeks) to every 42 days (6 weeks).

^c Consent may be taken prior to 28-day window if required,

^d Taken following progression on the latest line of therapy. The collection of this tumour tissue sample for central mutation analysis is not included in the 28-day screening period.

^e The optional second tumour tissue sample can be taken as part of the same procedure as the mandatory screening biopsy for mutation analysis.

^f Archival tumour sample only to be submitted after T790M positive status confirmed by central testing. Not required for T790M negative patients.

^g To be completed pre-dose.

^h If screening assessments are not done at Visit 2, but have been done at Visit 1 and have been performed within 14 days window prior to starting study treatment, with no change in condition and no clinical indication to do so, they do not have to be repeated on Visit 2 if subject's condition has not changed. (except for fasting glucose).

ⁱ To be taken at the same time as the screening biopsy is taken or prior to mutation screening. All plasma samples are required by AstraZeneca, regardless of the outcome of the mutation screening.

^j Collect every 6 weeks up to and including progression (corresponding with the RECIST assessments – and continuing after treatment discontinuation in absence of disease progression).

^k If for any reason the sample is not drawn prior to first dose it may be taken at any visit until the last study visit.

^l To be obtained at one time point at any time from Cycle 2 Day 1 onwards

^m If only one measurable lesion exists, it is acceptable to be used as long as it has not been previously irradiated, and baseline tumour assessment scans are done at least 14 days after the screening biopsy is performed.

ⁿ Assess every 6 weeks relative to first dose until end of study (including survival follow-up period) and at the time of progression.

^o Assess every 3 weeks relative to first dose until end of study (including survival follow-up period) and at the time of progression.

^p PRO-CTCAE will only be administered in those countries where a linguistically validated version exists.

^q Assessed at Cycle 7 Day 1 then every 3 weeks relative to first dose thereafter until end of study (including survival follow-up period) and at the time of progression.

^r Following AZD9291 discontinuation, SAEs considered related to study procedures should continue as outlined in Table 6.

^s Survival status including anti-cancer treatment to be performed every 6 weeks (relative to first dose) following disease progression or withdrawal from treatment.

^t Record subsequent response/progression data every 6 weeks until first confirmed disease progression on a subsequent treatment.

^u Discontinuation biopsy can be taken at discontinuation or progression, whichever comes first

^v If the patient has received CT/MRI scan before signing the ICF, and within 28 days prior to treatment, the assessment can still be acceptable if the scan meets the RECIST 1.1 criteria.

^w A photograph with proper identification cover may be taken by site and shared with Sponsor if the patient has a rash, or changes to eyelashes, skin or eyes during the study.

^x For patients participating biomarker/genetic research and from outside of China, HBV and HIV tests are needed for sample shipment purpose, and results should be negative.

^y Fasting glucose during Cycle 1 only (3 visits, C1D1, D8 and D15). And from cycle 2 onwards (visit will occur only on Day 1 for each cycle) random glucose will be collected

^z Visit windows are always calculated in relation to Cycle 1, Day 1.

Table 2 Study Plan - After 24 months Post LSFD until Final DCO^a

Visit	Treatment post 24 months every 84 days (12 weeks)	Treatment Discontinuation	Follow-up Period			For details see Protocol Section
	10+		28-day follow-up	Progression follow-up	Survival follow-up	
Cycle ^b / Day	D1	NA	NA	NA	NA	
Window (days)	±7	0	±7	±7	±7	SECTION:
Optional tumour biopsy for exploratory research		X		X		5.6
Physical examination, including weight	X	X				5.2.3 & 5.2.6.2
WHO Performance status	X	X				4.1
Pregnancy test (pre-menopausal females only)	as clinically indicated					5.2.1
Ophthalmologic assessment	← as clinically indicated →					5.2.7.1
Vital signs ^c	X					5.2.6
Digital ECG	X	X				5.2.4
Echocardiogram/MUGA	← every 12 weeks (±1 week) related to first dose →					5.2.5
Clinical chemistry/ Haematology/Urinalysis ^c	X	X				5.2.1
Echocardiogram/MUGA	X					5.2.5
Plasma sample for ctDNA ^c	X					4.3.3 & 5.6.2

Table 2 Study Plan - After 24 months Post LSFD until Final DCO^a

Visit	Treatment post 24 months every 84 days (12 weeks)	Treatment Discontinuation	Follow-up Period			For details see Protocol Section
	10+		28-day follow-up	Progression follow-up	Survival follow-up	
Cycle ^b / Day	D1	NA	NA	NA	NA	
Window (days)	±7	0	±7	±7	±7	SECTION:
Optional genetic consent and sample	X ^d					5.5
Optional CSF sample	X (once only) ^e					5.4.1
Tumour assessments (RECIST v1.1)	← X (every 12 weeks until disease progression) ^f →					4.2 & 5.1.1
EORTC QLQ-C30 and EQ-5D-5L (by electronic device)	← X (every 6 weeks until end of study and at the time of progression) relative to first dose →					5.3.2.1 & 5.3.2.2
EORTC QLQ LC13 (by electronic device)	← X (every 3 weeks until end of study and at the time of progression) relative to first dose →					5.3.2.1
PRO-CTCAE (by electronic device)	← X (every 3 weeks until end of study and at the time of progression) relative to first dose →					5.3.2.3
Healthcare Resource Use	← →					5.3.2.5
Dispense study medication	X					3.3 & 7.2
Dose with AZD9291	Daily dosing					7.2
Concomitant medication & procedures	← →					7.7

